## 1. REPORTING & ANALYSIS PLAN SYNOPSIS

Overview	Key Elements of the RAP
Purpose	
The purpose of this reporting and analysis plan (RAP) is to describe:
 
 
Any planned analyses and output to be included in the clinical study report for Protocol 204847.
 

Protocol	
 
This RAP is based on the original protocol (Dated: 18-FEB-2016) of study 204847 (GSK Document No. : 2015N257523_00).
 

Primary Objective	
 
For Part 1, to investigate the safety and tolerability of GSK3342830 after administration of single IV doses in healthy adult subjects
 
For Part 2, to investigate the safety and tolerability of GSK3342830 after administration of repeat IV doses in healthy adult subjects
 
For Part 3, to investigate the safety and tolerability of GSK3342830 after administration of a single IV dose in healthy adult Japanese subjects
 

Primary Endpoint	
 
Clinical safety data from adverse events (AEs), clinical laboratory tests, vital signs (blood pressure, heart rate, temperature, and respiration rate), and 12-lead electrocardiogram (ECG) readings
 

Study Design	
 
This is a Phase I, first-time-in-human (FTIH), randomized, double-blind (sponsor unblinded), single-center, placebo-controlled, dose-escalation study to determine the safety, tolerability, and pharmacokinetic (PK) profile of GSK3342830 after administration of single (Part 1) and repeat (Part 2) IV doses in healthy adult subjects, and after administration of a single IV dose in healthy adult Japanese subjects (Part 3).
 
Dose escalation will be conducted only if it is supported by the preliminary safety, tolerability, and PK results from the preceding dose levels in the study. This is the first administration of GSK3342830 in humans; therefore, as preliminary safety, tolerability, and PK results are reviewed internally at GSK and with the clinical study site, study design adjustments may be made based on emerging data from each dose cohort.
 
The repeat dose escalation component (Part 2) of this study is planned to be initiated after completion and evaluation of the all single dose cohorts up to and including 4000 mg. Initiation of Part 2 will be based on the evaluation of preliminary safety, tolerability, and PK data from the single dose escalation (Part 1) cohorts once safety at an exposure that exceeds the daily exposure predicted for the Part 2 planned starting dose of 1000 mg TID is demonstrated, which is predicted to occur at the 4000 mg single dose.
 
The single dose administration in Japanese subjects component (Part 3) of this study is planned to be conducted in parallel with Part 2. The dose for the Part 3 cohort will be based on preliminary safety and tolerability results of doses determined to be safe and well tolerated in subjects of non-Japanese heritage after completion of the single escalation dose cohorts (Part 1).
 

Planned	
 
Safety and PK data will be presented in tabular and/or graphical format and
 

Overview	Key Elements of the RAP
Analyses	summarized descriptively according to GSK's Integrated Data Standards Library (IDSL) standards.
Analysis Populations	
 
● Safety Population – defined as all subjects who receive at least 1 dose of study drug and have at least 1 post-dose safety assessment.
 
● PK Population - defined as all subjects who receive at least 1 dose of GSK3342830 and have evaluable PK data for GSK3342830.
 
● PK Parameter Population - defined as all subjects in the PK population for whom valid and evaluable PK parameters were derived.
 

Hypothesis	
 
● No inferential hypothesis testing will be performed on the safety variables.
 
● Dose proportionality of AUC(0-∞) and Cmax on Day 1 and for repeat dose groups AUC(0-τ) and Cmax of GSK3342830 on Day 15 will be assessed separately by day using the following power model:  <math display="block">y = a * \text{dose}^\beta</math> 
where y denotes the PK parameter being analyzed and a depends on the random error in the repeat dose phase where subjects take the study drug in a parallel-group fashion. Dose proportionality implies that <math>\beta=1</math> and will be assessed by estimating <math>\beta</math> along with its 90% CI. The exponent, <math>\beta</math>, in the power model will be estimated by regressing the loge-transformed PK parameter on loge-transformed dose.
 <math display="block">\log(y)=\log(a) + \beta * \log(\text{dose})</math> 
The power model will be fitted by restricted maximum likelihood (REML) using Statistical Analysis Software (SAS) Proc Mixed, with a fixed effect term for dose. The PK parameter endpoint and the factor dose will be loge-transformed prior to the analysis.
 
 
● For the repeat dose cohorts (Part 2), the time invariance ratio will be assessed by fitting a mixed effect model for AUC(0-∞) on Day 1 and AUC(0-τ) on Day 15 data with subject as a random effect and group (group=1 for AUC(0-∞) on Day 1, and group=2 for AUC(0-τ) on Day 15) as a fixed effect for each cohort.
 
● For the repeat dose cohorts (Part 2), the accumulation ratio (Ro) will be calculated as the ratio of AUC(0-τ) on Day 15 to AUC(0-τ) on Day 1 for each subject. The dosing interval (τ) will be equal to 8 hours. Following log-transformation, AUC(0-τ) of GSK3342830 on Days 1 and 15 will be analyzed by a mixed effect model, fitting dose, day, and dose-by-day interaction as fixed effects and subject as a random effect. For each dose, point estimate and 90% CI for the difference “AUC(0-τ) on Day 15 - AUC(0-τ) on Day 1” will be constructed using the appropriate error term. The point estimate and associated 90% CI will then be exponentially back-transformed to provide point and 90% CI estimates for the ratios “AUC(0-τ) on Day 15: AUC(0-τ) on Day 1.” If dose-by-day interaction is not significant, then a single point estimate and 90% CI pooled across all doses for the ratio AUC(0-τ) on Day 15: AUC(0-τ) on Day 1
 

Overview	Key Elements of the RAP
	
may be constructed with all estimates for each dose.
 

• To evaluate whether steady state was achieved, statistical analysis of steady-state <math>C_{\tau}</math> will be performed after log-transformation of <math>C_{\tau}</math> on Days 3, 6, 9, 12, 13, and 15. A mixed effect model will be fitted by dose and day (as a continuous covariate) as a fixed effect term and subject as a random effect term. Distributional assumptions underlying the statistical analyses will be assessed by visual inspection of residual plots. Normality will be examined by normal probability plots, while homogeneity of variance will be assessed by plotting the residuals against the predicted values for the model. Alternative analyses of the data will be performed if any of the model assumptions appear to be violated.

## 2. SUMMARY OF KEY PROTOCOL INFORMATION

### 2.1. Changes to the Protocol Defined Statistical Analysis Plan

Not applicable.

### 2.2. Study Objective(s) and Endpoint(s)

Objectives	Endpoints
Part 1	
Primary Objectives	Primary Endpoints

 
To investigate the safety and tolerability of GSK3342830 after administration of single IV doses in healthy adult subjects
 
	
 
Clinical safety data from AEs, clinical laboratory tests, vital signs (blood pressure, heart rate, temperature, and respiration rate), and 12-lead ECG readings
 

Secondary Objectives	Primary Objectives

 
To determine the pharmacokinetics of GSK3342830 after administration of single IV doses in healthy adult subjects
 
	
 
Plasma and urine concentrations PK endpoints include AUC(0-t), AUC(0-∞), Cmax, Tmax, CL, Vss, t1/2, Feu(t1-t2), Ae, and CLr of GSK3342830, as data permit
 

 
To assess dose proportionality of GSK3342830 after administration of single IV doses in healthy adult subjects
 
	
 
Pharmacokinetic endpoints include AUC(0-t), AUC(0-∞), and Cmax of GSK3342830 after administration of single IV doses for the assessment of dose proportionality, as data permit
 

Exploratory Objectives	Exploratory Endpoints

 
To correlate PK parameters (AUC[0-t], AUC[0-∞], and Cmax) of GSK3342830 with safety findings after administration of single IV doses in healthy adult subjects
 
	
 
Exposure-response analyses, as data permit
 

 
To evaluate the production of any GSK3342830 metabolites in plasma and urine and determine the need to perform a more detailed analysis of any metabolites
 
	
 
Metabolite characterization in plasma and urine and estimation of observed drug-related material in plasma to determine the presence of any metabolite >10%, and estimate the percentage dose eliminated via urine
 

Part 2	
Primary Objectives	Primary Endpoints

 
To investigate the safety and tolerability of GSK3342830 after administration of repeat IV doses in healthy adult subjects
 
	
 
Clinical safety data from AEs, clinical laboratory tests, vital signs (blood pressure, heart rate, temperature, and respiration rate), and 12-lead ECG readings
 

Secondary Objectives	Secondary Endpoints

 
To determine the pharmacokinetics of GSK3342830 after administration of repeat IV doses in healthy adult subjects
 
	
 
Plasma and urine concentrations and PK endpoints include AUC(0-t) and AUC(0-∞) on Day 1 only, AUC(0-τ), Cmax, Tmax, CL, Vss, t1/2, Cτ, Feu(t1- t2), Ae, and CLr of GSK3342830, as data permit
 

 
To assess dose proportionality of GSK3342830 after administration of repeat IV doses in healthy adult subjects
 
	
 
Pharmacokinetic endpoints include AUC(0-τ) and Cmax of GSK3342830 after administration of repeat IV doses for the assessment of dose proportionality, as data permit
 

Objectives	Endpoints

 
To examine the extent of accumulation, time invariance, and achievement of steady-state of GSK3342830 after administration of repeat IV doses in healthy adult subjects
 
	
 
Observed accumulation ratio (Ro) based on AUC and Cmax of GSK3342830 after administration of repeat IV doses, as data permit
 
Steady-state ratio (Rss) of GSK3342830 to assess time invariance, as data permit
 
Trough plasma concentrations at the end of the dosing interval (Cτ) to assess the achievement of steady-state of GSK3342830 after administration of repeat IV doses, as data permit
 

Exploratory Objectives	Exploratory Endpoints

 
To correlate PK parameters (AUC[0-t], AUC[0-∞], AUC[0-τ], and Cmax) of GSK3342830 with safety findings in healthy adult subjects after administration of repeat IV doses
 
	
 
Exposure-response analyses, as data permit
 


 
To evaluate the production of any GSK3342830 metabolites in plasma and urine and determine the need to perform a more detailed analysis of any metabolites
 
	
 
Metabolite characterization in plasma and urine and estimation of observed drug-related material in plasma to determine the presence of any metabolite >10%, and estimate the percentage dose eliminated via urine
 

Part 3	
Primary Objectives	Primary Endpoints

 
To investigate the safety and tolerability of GSK3342830 after administration of a single IV dose in healthy adult Japanese subjects
 
	
 
Clinical safety data from AEs, clinical laboratory tests, vital signs (blood pressure, heart rate, temperature, and respiration rate), and 12-lead ECG readings
 

Secondary Objectives	Secondary Endpoints

 
To determine the pharmacokinetics of GSK3342830 after administration of a single IV dose in healthy adult Japanese subjects
 
	
 
Plasma and urine concentrations PK endpoints include AUC(0-t), AUC(0-∞), Cmax, Tmax, CL, Vss, t1/2, Feu(t1-t2), Ae, and CLr of GSK3342830, as data permit
 

Exploratory Objectives	Exploratory Endpoints

 
To correlate PK parameters (AUC[0-t], AUC[0-∞], and Cmax) of GSK3342830 with safety findings in healthy adult Japanese subjects after administration of repeat IV doses
 
	
 
Exposure-response analyses, as data permit
 

 
To evaluate the production of any GSK3342830 metabolites in plasma and urine and determine the need to perform a more detailed analysis of any metabolites
 
	
 
Metabolite characterization in plasma and urine and estimation of observed drug-related material in plasma to determine the presence of any metabolite >10%, and estimate the percentage dose eliminated via urine
 

### 2.3. Study Design

Overview of Study Design and Key Features	
Part 1 Single Dose Escalation Study Design Schematic	

Note: Figure shows illustration of the planned doses, which may be switched, changed, or cancelled based on preliminary safety, tolerability, and pharmacokinetic data from preceding cohorts.
	
Part 2 Repeat Dose Escalation Study Design Schematic	

Note: Figure shows illustration of the planned doses, which may be switched, changed, or cancelled based on preliminary safety, tolerability, and pharmacokinetic data from preceding cohorts.
	
Design Features	
 
Part 1 is planned to include 6 dose level cohorts. Up to 2 additional doses (1 per cohort) may be evaluated to further understand the study drug. The planned starting GSK3342830 dose in Part 1 is 250 mg administered as a single IV infusion. The dose is planned to increase in subsequent cohorts to 500, 1000, 2000, 4000, and ≤6000 mg IV. In Part 1, subjects will remain confined to the clinical unit from admission on Day -1 until all scheduled safety and PK assessments have been completed on Day 3. The duration of study (from Screening to the Follow-up visit) for each subject will be up to approximately 43 days.
 
Part 2 is planned to include a sequential panel of up to 3 dose level cohorts. Additional repeat dose cohorts may be evaluated to further assess the safety, tolerability, and pharmacokinetics of GSK3342830. The planned starting GSK3342830 dose in Part 2 is 1000 mg administered as a single IV infusion on Day 1, TID IV infusions on Days 2, 3, 4, 5, 6, 7, 8, 9, 10, 11, 12, 13, and 14, and a single IV infusion on Day 15. The dose is planned to increase in subsequent cohorts to 2000 and 4000 mg TID. In Part 2, subjects will remain confined to the clinical unit from admission on Day -1 until after all scheduled safety assessments have been completed on Day 16. The duration of study (from Screening to the Follow-up visit) for each subject will be up to approximately 56 days.
 
Part 3 is planned to include 1 cohort (Cohort J). The planned GSK3342830 dose in Part 3 will be either 250, 500, 1000, 2000, 4000, or ≤6000 mg based on preliminary safety and tolerability results of doses determined to be safe and well tolerated in subjects of non-Japanese heritage after completion of the single escalation dose cohorts (Part 1). The dose in Part 3 will be
 

Overview of Study Design and Key Features	
	
administered as a single IV infusion on Day 1.
 
In Part 3, subjects will remain confined to the clinical unit from admission on Day -1 until all scheduled safety and PK assessments have been completed on Day 3. The duration of study (from Screening to the Follow-up visit) for each subject will be up to approximately 43 days.

Dosing	
 
For Part 1, doses are planned to escalate in a sequential fashion contingent on the safety, tolerability, and PK profile of approximately 4 subjects who received active treatment in the previous cohort. The evaluated subjects should be followed for a minimum of 48 hours after dosing. Dose escalations or reductions will progress with modifications based on the preliminary safety, tolerability, and PK data from the preceding cohorts.
 
For Part 2, doses are planned to escalate in a sequential fashion based on the preliminary safety, tolerability, and PK data from Part 1 and at least 14 days of repeat dosing in approximately 5 subjects who received active treatment in the previous cohort in Part 2. The evaluated subjects should be followed for a minimum of 24 hours after dosing on Day 15. The dosing frequency, duration of dosing, and decision to dose in the next dose level may be changed based on the safety, tolerability, or PK findings in Part 1 or earlier doses in Part 2.
 
The dose in Part 3 will be administered as a single IV infusion on Day 1.
 

Treatment Assignment	
 
For Part 1 on Day 1, before study drug administration, subjects will be randomized to treatment with either GSK3342830 or placebo in a 3:1 ratio. As a safety precaution, all Part 1 cohorts will be split into 2 sub-cohorts for sentinel dosing. In each cohort, the first 2 subjects will receive either GSK3342830 or placebo (1 active/1 placebo). Dosing in the remaining 6 subjects (5 active/1 placebo) in that cohort will occur at least 24 hours later based on the safety results from the first sub-cohort.
 
For Part 2 on Day 1, before study drug administration, subjects will be randomized to treatment with either GSK3342830 or placebo in a 4:1 ratio.
 
For Part 3 on Day 1, before study drug administration, subjects will be randomized to treatment with either GSK3342830 or placebo in a 4:1 ratio.
 

Interim Analysis	
 
No formal interim analysis. However, during dose escalation, Bayesian analysis is performed to produce inferences about model parameters and the predictive probability that an individual will have certain PK parameters larger than prespecified thresholds at for each dose level to aid the next dose selection.
 

## 2.4. Statistical Hypotheses

No inferential hypothesis testing will be performed.

### 3. PLANNED ANALYSES

#### 3.1. Interim Analyses

No formal interim analysis is planned for this study. However, one may be conducted in the event of clinically significant safety or PK findings. All preliminary safety, tolerability, and available PK data will be reviewed internally at GSK and with the clinical study site before each dose escalation in Part 1, before initiation of Part 2, and before each dose escalation in Part 2.

The relationship between dose and plasma GSK3342830 exposure, and associated variability will be characterized by a power model once data are available from 3 dose levels. Prior to that, prediction of the human exposure at the next dose will be based on population PK modeling (if feasible) or on the assumption of dose–exposure proportionality (i.e., doubling the dose gives an approximate doubling of exposure). If prior PK results show less than proportional increase in exposure with increasing dose, the prediction will be based on the assumption that the fold exposure increase to fold dose increase ratio will be the same with the current dose escalation as it was with the previous one. If prior PK results show more than proportional increase in exposure with dose, subsequent dose escalations will not be higher than 3-fold. The power model will be updated as data become available throughout the study. During dose escalation, Bayesian inferential probability that a group mean will have AUCs (AUC[0-t] for single dose and AUC[0-8]x3 as AUC[0-24] for repeat dose) and Cmax values greater than 2875 h•µg/mL and 2270 µg/mL (mean exposures at the NOAEL dose in the rat and monkey), respectively, and Bayesian predictive probability that an individual will have AUC(0-24) and Cmax values greater than 3460 h•µg/mL and 2590 µg/mL (maximum exposures at the NOAEL dose in the rat for AUC and the monkey for Cmax), respectively, may be calculated for the next dose level and used together with safety and tolerability data to aid the next dose selection.

#### 3.2. Final Analyses

The final planned primary analyses will be performed after the completion of the following sequential steps:

1. All subjects have completed the study as defined in the protocol.
2. All required database cleaning activities have been completed and final database release and database freeze has been declared by Data Management.
3. All criteria for unblinding the randomisation codes have been met.
4. Randomisation codes have been distributed according to PPD procedures.

### 4. ANALYSIS POPULATIONS

Population	Definition / Criteria	Analyses Evaluated
Safety	
 
Defined as all subjects who receive at least 1 dose of study drug and have at least 1 post-dose safety assessment.
 
	
 
Study Population
 
Safety
 

Population	Definition / Criteria	Analyses Evaluated
	
 
This population will be based on the treatment the subject was randomized to receive.
 
	
Pharmacokinetic	
 
Defined as all subjects who receive at least 1 dose of GSK3342830 and have evaluable PK data for GSK3342830.
 
	
 
PK
 

Pharmacokinetic Parameter	
 
Defined as all subjects in the PK population for whom valid and evaluable PK parameters were derived
 
	
 
PK Parameter
 

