6.7. Compliance with Study Treatment Administration

When the individual dose for a subject is prepared from a bulk supply, the preparation of the dose will be confirmed by a second member of the study site staff.

Subjects will be dosed at the clinical unit and receive study treatment directly from the investigator or designee, under medical supervision. The date and time of each dose administered in the clinical unit will be recorded in the source documents. The dose of study treatment and study subject identification will be confirmed at the time of dosing by a member of the study site staff other than the person administering the study treatment.

GSK3342830 and placebo will be administered intravenously to subjects at the site. Administration will be documented in the source documents and recorded in the electronic case report form (eCRF).

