9.4. Key Elements of Analysis Plan

9.4.1. Primary Analyses

Safety Analyses

The following safety evaluations will be performed:

- Monitoring for AEs
- Routine clinical laboratory tests including chemistry, hematology, and urinalysis
- Vital signs
- Twelve-lead ECG readings
- Continuous cardiac monitoring (dual-lead telemetry)

Safety endpoints will include AEs, clinical laboratory test results (chemistry [including liver function parameters], hematology, and urinalysis), vital signs (BP, heart rate, respiratory rate, and body temperature), and 12-lead ECG readings.

All safety data will be presented in data listings. Subject demographics, medical history, and prior and concomitant medications will be summarized for each dose level using descriptive statistics. For continuous variables, these summaries will include number of subjects, mean, median, standard deviation, minimum, and maximum.

For categorical variables, the summaries will include frequencies and corresponding percentages. No inferential hypothesis testing will be performed on the safety variables.

Adverse events will be coded using the MedDRA classification system.

Treatment-emergent AEs will be defined as any AEs, regardless of relationship to study drug, that occur after the dose of study drug until the Follow-up visit. The treatment-emergent AEs will be summarized for each dose level at AE onset for the overall number of AEs and percentage of subjects who experience them. The total number of AEs will be summarized by dose level and overall. The AEs will be further summarized by severity and relationship to the study drug. If relationship information is missing, the AE will be considered treatment related. Listings for the subsets of SAEs

and treatment-related SAEs will be provided. The SAEs and number of AEs leading to discontinuation will be summarized. The incidence of AEs will also be summarized by system organ class and preferred term.

Clinical laboratory test results, vital signs, and 12-lead ECG results will be summarized by actual values and change from baseline. Clinical laboratory values that are outside of the reference ranges will be flagged and evaluated for clinical significance by the investigator. Any 12-lead ECG abnormalities will be summarized by each dose level. Physical examination findings and cardiac telemetry results will be listed.

Detailed descriptions of the analyses in this study will be presented in the RAP.

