## 7. PRIMARY STATISTICAL ANALYSES

### 7.1. Safety Analyses

#### 7.1.1. Overview of Planned Safety Analyses

The safety analyses will be based on the Safety population, unless otherwise specified.

Table 3 provides an overview of the planned Safety analyses, with full details of data displays being presented in Appendix 11: List of Data Displays.

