### 10.3.3. Reporting Process & Standards

Reporting Process
Software

 
• The currently supported versions of SAS software [Insert Other Software as Required] will be used.
 

Analysis Datasets

 
• Analysis datasets will be created according to CDISC standards (SDTM IG Version 3.1.3 & AdaM IG Version 1.0).
 
• For creation of ADaM datasets (ADCM/ADAE), the same version of dictionary datasets will be implemented for conversion from SI to SDTM.
 

Generation of RTF Files

 
• RTF files will be generated for all reporting efforts described in the RAP.
 

Reporting Standards
General

Reporting Standards	

 
• The current GSK Integrated Data Standards Library (IDSL) will be applied for reporting, unless otherwise stated:             
 
○ 4.03 to 4.23: General Principles
 
○ 5.01 to 5.08: Principles Related to Data Listings
 
○ 6.01 to 6.11: Principles Related to Summary Tables
 
○ 7.01 to 7.13: Principles Related to Graphics
 
 
 
	
Formats	

 
• All data will be reported according to the actual treatment the subject received unless otherwise stated.
 
• GSK IDSL Statistical Principles (5.03 & 6.06.3) for decimal places (DP's) will be adopted for reporting of data based on the raw data collected.
 
• Numeric data will be reported at the precision collected on the eCRF.
 
• The reported precision from non eCRF sources will follow the IDSL statistical principles but may be adjusted to a clinically interpretable number of DP's.
 
	
Planned and Actual Time	

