## 10.11.5. Safety Tables

Safety : Tables					
No.	Population	IDSL / TST ID / Example Shell	Title	Programming Notes	Deliverable [Priority]
Adverse Events					
2.1	Safety	AE2	Relationship of Adverse Event System Organ Classes, Preferred Terms and Verbatim Text		SAC [1]
2.2	Safety	AE1	Summary of All Adverse Events		SAC [1]
2.3	Safety	AE1	Summary of Drug-Related Adverse Events		SAC [1]
2.4	Safety	A15	Summary of Common (>=5%) Non-serious Adverse Events by System Organ Class and Preferred Term (Number of Subjects and Occurrences)		SAC [1]
2.5	Safety	A16	Summary of Serious Adverse Events by System Organ Class and Preferred Term (Number of Subjects and Occurrences)		SAC [1]
Laboratory Measurements					
2.6	Safety	LB1	Summary of Clinical Chemistry Values		SAC [1]
2.7	Safety	LB1	Summary of Clinical Chemistry Change from Baseline		SAC [1]
2.8	Safety	LB1	Summary of Haematology Values		SAC [1]
2.9	Safety	LB1	Summary of Haematology Change from Baseline		SAC [1]
2.10	Safety	UR3b	Summary of Urinalysis Dipstick Results		SAC [1]
Electrocardiograms					
2.11	Safety	EG1	Summary of ECG Findings		SAC [1]
2.12	Safety	EG2	Summary of ECG Values		SAC [1]
2.13	Safety	EG2	Summary of Change from Baseline in ECG Values		SAC [1]
2.14	Safety	SAFE_T1	Summary of Frequency of Maximum Post-Dose ECG Parameter Corrected QTc Interval		SAC [1]

Safety : Tables					
No.	Population	IDSL / TST ID / Example Shell	Title	Programming Notes	Deliverable [Priority]
2.15	Safety	SAFE_T2	Summary of Frequency of Maximum Change from Baseline for ECG Parameter Corrected QTc Interval		SAC [1]
Vital Signs					
2.16	Safety	VS1	Summary of Vital Signs		SAC [1]
2.17	Safety	VS1	Summary of Vital Signs Change from Baseline		SAC [1]

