## 10.11.9. ICH Listings

ICH : Listings					
No.	Population	IDSL / TST ID / Example Shell	Title	Programming Notes	Deliverable [Priority]
Randomisation					
1	Safety	TA1	Listing of Randomized and Actual Treatments		SAC [1]
Subject Disposition					
2	Safety	ES2	Listing of Reasons for Study Withdrawal		SAC [1]
3	Screened	ES7	Listing of Reasons for Screening Failure		SAC [1]
4	Screened	DV2	Listing of Important Protocol Deviations		SAC [1]
5	Safety	IE3	Listing of Subjects with Inclusion/Exclusion Criteria Deviations		SAC [1]
Demographics					
6	Safety	DM2	Listing of Demographic Characteristics	Include height, weight, BMI, Smoking History, Alcohol History, Caffeine History, and Drug Use History	SAC [1]
7	Safety	DM9	Listing of Race		SAC [1]
Medical Conditions and Concomitant Medications					
8	Safety	MH2	Listing of Medical Conditions		SAC [1]
9	Safety	CM3	Listing of Concomitant Medications		SAC [1]
Exposure					
10	Safety	SAFE_L1	Listing of Exposure Data		SAC [1]
Safety					
11	Safety	AE7	Listing of Subject Numbers for Individual Adverse Events		SAC [1]

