*Note to programmer: Continue for all treatments in Part 1, Part 2, and Part 3. Present Part 2 and Part 3 on separate pages.*

---

GlaxoSmithKline  
Example : AE2  
Protocol : 204847  
Population : Safety

Table 2.1  
Relationship of Adverse Event System Organ Classes, Preferred Terms and Verbatim Text

---

System Organ Class	Preferred Term	Verbatim Text
SOC #1	Preferred Term # 1	XXXXXXXXXX
	Preferred Term # 2	XXXXXXXXXX
	Preferred Term # 3	XXXXXXXXXX
	Preferred Term # 4	XXXXXXXXXX
SOC #2	Preferred Term # 1	XXXXXXXXXX
	Preferred Term # 2	XXXXXXXXXX
	Preferred Term # 3	XXXXXXXXXX
	Preferred Term # 4	XXXXXXXXXX

---

GlaxoSmithKline  
Example : AE1  
Protocol : 204847  
Population : Safety

Table 2.2  
Summary of All Adverse Events

Study Part: 1

System Organ Class Preferred Term	GSK3342830 250 mg (N=xx)	GSK3342830 500 mg (N=xx)	...	Total (N=xx)
Any Event	xx (xx.x%)	xx (xx.x%)	...	xx (xx.x%)
System Organ Class #1	xx (xx.x%)	xx (xx.x%)	...	xx (xx.x%)
Preferred Term #1	xx (xx.x%)	xx (xx.x%)	...	xx (xx.x%)
Preferred Term #2	xx (xx.x%)	xx (xx.x%)	...	xx (xx.x%)
Preferred Term #3	xx (xx.x%)	xx (xx.x%)	...	xx (xx.x%)

...

*Note to programmer: System Organ Class (SOC) is displayed in descending order of frequency for 'Overall' then alphabetically. Preferred Term is displayed in descending order of frequency for 'Overall' then alphabetically within SOC. Continue for all treatments in Part 1, Part 2, and Part 3. Present Part 2 and Part 3 on separate pages.*

---

At each level of subject summarization, a subject is counted once if the subject reported one or more events.

GlaxoSmithKline  
 Example : AE1  
 Protocol : 204847  
 Population : Safety

Table 2.3  
 Summary of Drug-Related Adverse Events

Study Part: 1				
System Organ Class Preferred Term	GSK3342830 250 mg (N=xx)	GSK3342830 500 mg (N=xx)	...	Total (N=xx)
Any Event	xx (xx.x%)	xx (xx.x%)	...	xx (xx.x%)
System Organ Class #1	xx (xx.x%)	xx (xx.x%)	...	xx (xx.x%)
Preferred Term #1	xx (xx.x%)	xx (xx.x%)	...	xx (xx.x%)
Preferred Term #2	xx (xx.x%)	xx (xx.x%)	...	xx (xx.x%)
Preferred Term #3	xx (xx.x%)	xx (xx.x%)	...	xx (xx.x%)

...

*Note to programmer: System Organ Class (SOC) is displayed in descending order of frequency for 'Overall' then alphabetically. Preferred Term is displayed in descending order of frequency for 'Overall' then alphabetically within SOC. Continue for all treatments in Part 1, Part 2, and Part 3. Present Part 2 and Part 3 on separate pages.*

---

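### SAP Section 4 leaves open whether final safety tables place an individually mis-dosed subject under the randomised or the received treatment, and it reads most naturally as randomised

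*SAP*

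**What the plan says.** - **SAP Section 4** admits a subject to the Safety Population on two conditions: at least one dose, and at least one safety assessment after it. It then adds: "This population will be based on the treatment the subject was randomized to receive". The same table row assigns this population to the Study Population analyses as well as to Safety.
- **SAP 7.1.1**: "The safety analyses will be based on the Safety population, unless otherwise specified".
- **SAP 10.3.3**, under Formats: "All data will be reported according to the actual treatment the subject received unless otherwise stated".
- **Protocol 9.3.1** gives the same two membership conditions and is silent on grouping. **Protocol 9.4.1** adds, for adverse events: "The treatment-emergent AEs will be summarized for each dose level at AE onset". **SAP 2.1** declares no change from the protocol's analysis plan.
- **SAP 10.11.5** leaves the Programming Notes column blank from Table 2.2 ("Summary of All Adverse Events") to Table 2.17 and marks every one of these tables as a final (SAC) deliverable. The Table 2.2 shell says "Continue for all treatments in Part 1, Part 2, and Part 3" but not which treatment defines a column.
- **SAP 10.3.1** notes that outputs will carry the dose levels actually used, because the randomisation schedule names cohorts rather than doses.
- Dosing errors are foreseen. Listing 1 is the "Listing of Randomized and Actual Treatments", the Listing 10 shell asks whether the treatment given was correct, and the Table 1.4 shell has a deviation category for wrong treatment or dose.

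**The concern.** Safety is the primary objective in all three parts, and comparison with placebo is descriptive, made by reading across columns. In a first-in-human study with 6 to 8 active subjects per dose level, one subject in the wrong column can make a drug event look like background, or the reverse.

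The grouping rule should therefore be fixed before any dosing error is known. As written, the SAP contains one sentence pointing to randomised treatment and another pointing to actual treatment, and the second gives way to exceptions without saying whether the first is one. The choice could then be made after both the error and its outcome have been seen.

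**Working it through.** **Step 1: what the Section 4 sentence does.** Membership is already settled by dosing and a post-dose assessment, so the added sentence does no work as a membership rule. Its most natural function is to assign subjects to treatment groups. Because 10.3.3 yields to contrary statements, and 7.1.1 rests the safety analyses on this population, two readings follow:

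- *Section 4 is the exception.* Tables 2.2 to 2.17 are by randomised treatment, and a mis-dosed subject appears under a treatment or dose not received.
- *Section 4 only describes the population.* Then 10.3.3 governs, the tables are by actual treatment, and nothing is wrong.

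**Step 2: does other text decide?**

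- *Adverse events.* Protocol 9.4.1 works from dose level at onset, which suggests exposure, and SAP 2.1 claims no departure from the protocol. Together they point towards treatment received, although 9.4.1 does not use the words actual or received.
- *Laboratory, vital-sign and ECG tables.* No text settles these.
- *The 10.3.1 note.* It covers a change of dose for a whole cohort, not an error in one subject.
- *The PK Population.* It is defined by receipt of GSK3342830. Under the as-randomised reading, a placebo-randomised subject given active drug could count in the PK Population while their safety data sat under placebo. That would sit badly with the exposure-safety analyses in protocol 9.4.3.

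**Step 3: size, as illustration only.** The plan states no figure to reproduce. The inputs are the planned numbers in protocol 4.3: Part 1 has 6 cohorts, each with 6 active and 2 placebo. SAP 10.3.1 shows one placebo group for Part 1, so pooled placebo = 6 × 2 = 12. Part 3 has 8 active and 2 placebo. Assume one mis-dosed subject who has the only event.

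| Scenario | By randomised treatment | By actual treatment |
|---|---|---|
| Part 1 (a): randomised to placebo, given active | placebo 1/12 = 8.3%; active 0/6 | placebo 0/11; active 1/7 = 14.3% |
| Part 1 (b): randomised to active, given placebo | active 1/6 = 16.7%; placebo 0/12 | active 0/5; placebo 1/13 = 7.7% |
| Part 3: randomised to placebo, given active | placebo 1/2 = 50%; active 0/8 | placebo 0/1; active 1/9 = 11.1% |

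Now let others have the event too in case (a). With k other placebo events, the placebo shift is (k+1)/12 − k/11 = (11 − k)/132. With j other events at the active dose, the active shift is (j+1)/7 − j/6 = (6 − j)/42.

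- k = 0: 8.3 points; k = 1: 7.6 points (2/12 against 1/11); k = 11: 0.
- j = 0: 14.3 points; j = 1: 11.9 points (2/7 against 1/6); j = 6: 0.

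Without a dosing error, the two readings give identical tables.

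**Step 4: mixed exposure.** Part 2 schedules 1 + 13 × 3 + 1 = 41 infusions per subject (protocol 6.1). An error could affect some infusions and not others, so treatment actually received may not be a single value.

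**The case against.** The best defence is that the two SAP sections do different jobs. Section 4 defines populations and 10.3.3 governs displays, so the display rule controls the columns and a mis-dosed subject is shown by treatment received. A reader might infer a flat contradiction between the sections. The documents do not support that: if Section 4 is only descriptive, 10.3.3 simply applies. This part of the defence stands. It does not remove the ambiguity, because it leaves the Section 4 sentence with nothing to do, and 10.3.3 expressly allows exceptions.

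A reader might also infer that nothing in the plan bears on the question, or that the SAP plainly departs from the protocol. Both go too far. Protocol 9.4.1 with SAP 2.1 favours treatment received for adverse events, and a departure exists only under the as-randomised reading and only if dose level at onset means dose received. Cohort-level dose changes are already reported as actual.

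The defence is also right that the risk is low. Dosing is in a single unit under supervision. Under protocol 6.7 the dose and the subject's identity "will be confirmed at the time of dosing by a member of the study site staff other than the person administering the study treatment", and a second person confirms preparation from bulk supply. Listings 1 and 10 and Table 1.4 would expose an error, although they would not correct the summary tables.

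**Conclusion.** The point holds as an unresolved ambiguity of minor severity. On the more natural reading of Section 4, final safety Tables 2.2 to 2.17 would place an individually mis-dosed subject under a treatment or dose not received. On the other reading there is no error. The gap is clearest for laboratory, vital-sign and ECG tables, since the adverse-event text leans towards treatment received.

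The consequence needs both a subject-level dosing error and the as-randomised reading. The figures above assume planned cohort sizes and one mis-dosed subject with an event. They show how far small denominators can move, not how often this would happen.

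A reader might infer that escalation decisions are exposed. They are not: these tables are final deliverables, and the SAP's dose-escalation deliverables are pharmacokinetic. Nor is any inferential result at risk, because safety is not tested.

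**What to change.** 1. Replace the Section 4 sentence with: *For safety analyses, subjects will be analysed according to the treatment and dose level actually received.* This agrees with 10.3.3.
2. State separately whether Study Population Tables 1.1, 1.2 and 1.5 to 1.9 use randomised or received treatment. They use the same population, so changing the sentence would otherwise leave their basis unclear.
3. For a Part 2 subject with mixed exposure, summarise adverse events by treatment and dose level at onset, following protocol 9.4.1. For the other safety tables, pre-state one column rule and add a footnote. One option is the active dose level received for most infusions, if any active drug was given.
4. Keep Listings 1 and 10 so that any discrepancy stays visible.

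The cost is one replaced sentence, one added sentence for the Study Population tables, and a short mixed-exposure rule with its footnote. Actual treatment and the correctness of each dose are already collected for Listings 1 and 10, so no new data are needed.
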